3.2 Procedure and intervention (if applicable)

This is a retrospective study and all procedures have already been performed within standard care. In a retrospective dataset we compare two standard care strategies: THA and wait-and-see, in which patients did not receive THA and remain on the waiting list.

1.1 Duration of study

The study will be conducted with existing data starting from 1-4-2020 up until 31-3-2022. Patients on the waiting list for THA and with a completed intake questionnaire between 1-4-2020 and 1-1-2022 are included for this study and outcomes will be collected up until 31-3-2022. Mean follow-up time in days will be calculated for both the THA and non-surgery group. The timeline for this target trial emulation is presented in figure 2.

1.2 Recruitment and selection of subjects

1.2.1 Screening/selection

Retrospective data will be collected by [name] and the VBHC data analysts at OLVG and Martini hospital.

1.2.2 Study population
 
Patients with hip osteoarthritis that were on the waiting list for THA between 1-4-2020 and 1-1-2022 and had a completed intake questionnaire will be included. The number of patients is dependent on how many patients completed the questionnaires and needs to be investigated. However, based on the waiting list at the time and the number of performed surgeries in the two hospitals, we expect to include at least 100 patients in each cohort (THA group and non-surgery group). Since we use observational data for trial emulation, no sample size calculation is needed (8).

1.2.3 Inclusion criteria
 
Inclusion criteria:
 
 - Patients on the waiting list for primary THA between 1-4-2020 up to 31-3-2022 in OLVG or Martini hospital. - Completed intake questionnaire (HOOS-PS baseline) - Indication osteoarthritis of the hip

1.2.4 Exclusion criteria
 
Exclusion criteria:
 
 - Patients that received THA on both sides within follow-up (1-4-2020 and 1-1-2022) will be excluded. - Patients with other indications than osteoarthritis of the hip were excluded.

1.2.5 Number of subjects/ sample size
 
Since we use observational data for trial emulation no sample size calculation is needed (8). The participants are already exposed to an intervention or not. Differences in the primary and secondary outcomes (PROMs) between groups will be interpreted using 95% confidence intervals and thresholds for clinical relevance which are reported below.

1.3 Data collection: variables and measurement methods
 
1.3.1 Primary outcome measure (dependent variable)
 
Primary outcome is the change score for hip function measured with the HOOS-PS at 3-months postoperative in the THA group and at least 3-months post waiting list in the control group compared to baseline. The HOOS-PS is a 5-item questionnaire that quantifies hip disability. The raw outcome is converted to a Rasch-based interval score ranging from no difficulty (0) to extreme difficulty (100) (3,4,5). The minimal clinically important difference (MCID) for the HOOS-PS is 23 points (6). We will also calculate the minimal important change in our study population, based on an anchor question.


3.5.2. Secondary outcome measure
 
Secondary outcomes are change scores on other patient reported outcome measures (PROMs). Pain during weight bearing is measured on a numerical rating scale (NRS) ranging from 0-10. The minimal clinically important difference (MCID) for the NRS is 2 points. The anchor based questions range from 1-7 for functioning and pain. These PROMs were obtained at baseline (except the anchor based question) and at 3-months postoperatively and at least 3-months post waiting list

1.3.2 Overview of variables and measurement instruments

Variable	Measuring instrument/ Source of data	Outcome values	Measurement time
Sex	VBHC data (source is EHR*)	numeric (1 = F, 2 = M) 999 or NA is missing	Baseline
Age at time of inclusion	VBHC data (source is EHR*)	Numeric 999 or NA is missing	Baseline
Date for order THA	VBHC data (source is EHR*)	date (YYYY-MM-DD)	Baseline
Surgery date	VBHC data (source is EHR*)	date (YYYY-MM-DD) or not applicable (NA)	Date of surgery
Date completion of baseline questionnaire	VBHC data (source is EHR*)	date (YYYY-MM-DD)	Baseline
HOOS_PS_BL	HOOS_PS_PI VBHC data (source is EHR*)	HOOS-PS personal interval level score at baseline. Numeric (0-100) 999 or NA is missing	Baseline
Pain weight bearing at baseline	NRS VBHC data (source is EHR*)	numeric (0-10) 999 or NA is missing	Baseline
Patient followed physical therapy before hospital visit	VBHC data (source is EHR*)	No (0) / Yes (1) 999 or NA is missing	Baseline
Date completion of 3-months postoperative questionnaire	VBHC data (source is EHR*)	date (YYYY-MM-DD) or not applicable (NA)	3-months PO
Date completion of 3-months waiting list questionnaire	VBHC data (source is EHR*)	date (YYYY-MM-DD) or not applicable (NA)	≥ 3-months waiting list
HOOS_PS_3M_PO	HOOS_PS_PI VBHC data (source is EHR*)	HOOS-PS personal interval level score at 3-months postoperatively. Numeric (0-100) 999 or NA is missing	3-months PO
HOOS_PS_3M_WL	HOOS_PS_PI Waiting list questionnaire (source is EHR*)	HOOS-PS personal interval level score at 3-months waiting list. Numeric (0-100) 999 or NA is missing	≥ 3-months waiting list

Pain weight bearing at 3-months postoperatively	NRS VBHC data (source is EHR*)	numeric (0-10) 999 or NA is missing	3-months PO
Pain weight bearing at 3-months waiting list	NRS VBHC data (source is EHR*)	numeric (0-10) 999 or NA is missing	≥ 3-months waiting list
Anchor based question for pain postoperatively	Anchor	Numeric (1-7) 1= very much deteriorated 2= much deteriorated 3= slightly worsened 4= not changed 5= slightly improved 6= much improved 7= very much improved 999 = missing value	3-months PO
Anchor based question for function postoperatively	Anchor	Numeric (1-7) 1= very much deteriorated 2= much deteriorated 3= slightly worsened 4= not changed 5= slightly improved 6= much improved 7= very much improved 999 = missing value	3-months PO
Anchor based question for pain waiting list	Anchor	Numeric (1-7) 1= very much deteriorated 2= much deteriorated 3= slightly worsened 4= not changed 5= slightly improved 6= much improved 7= very much improved 999 = missing value	≥ 3-months waiting list
Anchor based question for function waiting list	Anchor	Numeric (1-7) 1= very much deteriorated 2= much deteriorated 3= slightly worsened 4= not changed 5= slightly improved 6= much improved 7= very much improved 999 = missing value	≥ 3-months waiting list

- EHR = Electronic health record.
- NRS = Numerical rating scale
- PO = postoperatively

1.4 Data analysis
1.4.1 Data inspection
Missing data will be defined in the database as 9999 or NA. Patients with a missing baseline HOOS-PS will not be included in the database. Extreme values will be explored by visual inspection such as boxplots and scatterplots. Extreme values will be verified and discussed in the research team before starting the analysis.
1.4.2 Analyses

 1. Measure if THA is effective to improve physical function in patients with osteoarthritis of the hip compared to non-surgery by means of RCT Target Trial Emulation. 2. Assessment to test the assumption that group allocation to the surgery group or non-surgery group cannot be explained by patient characteristics by means of logistic regression analysis. Secondly we test the assumption that follow-up time in days is similar between the two groups. 
1. Measure effect of THA: Two multiple regression analyses will be performed with the HOOS-PS and pain change score, respectively, as the dependent variable, and experimental condition (THA/ no-THA), age, sex, HOOS-PS score at baseline, pain score at baseline, physical therapy before baseline (yes/no) and follow-up time in days as independent variables. All regression coefficients and their 95% confidence intervals will be provided. Differences will be considered statistically significant when $p \leq 0.05$ and clinically relevant when differences exceed the MCID of 23 points for the HOOS-PS and 2 points for the NRS (6,7).
 
Descriptives on all independent variables will be presented and assessed by visual inspection of boxplots (for continuous variables) or tables (for categorical variables). These results will be provided for transparency purposes.
 
2. Test whether assumptions for target trial emulation are met. A logistic regression analysis will be performed on patients within the VBHC data set between 1-4-2020 and 1-1-2022 to check whether the group allocation cannot be explained by patient characteristics. Group being the dependent variable (THA vs. non-surgery) and age (continuous), sex (M/F), physical therapy before the hospital visit (yes/no), follow-up time in days (continuous), pain at baseline (NRS, continuous) and the HOOS-PS at baseline (continuous) will be included in the model as independent variables. Results will be considered statistically significant when $p \leq 0.05$. In case an independent variable has a statistically significant effect on the outcome, clinical relevance will be considered and discussed for the effect size on chance to be allocated to the THA or non-surgery group. Secondly, we will test the assumption that follow-up time in days is not statistically significantly different between the THA and non-surgery group. Follow-up time is defined by calculating the number of days between the date of the orthopedic visit) and the date of the follow-up questionnaire.

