Within the COVID period there were various periods of scaling up and down surgical capacity for elective hip operations, caused by external factors. For example, patient A, scheduled for surgery on Tuesday, proceeded, while patient B, scheduled for Thursday, had to be rescheduled due to changed government or regional policy effective the next day. Patient C had surgery while patient D was cancelled because the surgeon suddenly had to quarantine due to a child or partner with a COVID infection. These issues caused that in some patients THA could be performed and in other patients THA was cancelled.

We assume that whether or not such surgeries took place during the COVID period was beyond the control of patients, doctors and researchers and can be seen as a form of (pseudo)randomization. In a traditional RCT, randomization is done by means of computerized random sequence generation. In an emulation trial (1, 11), randomization is introduced by factors outside of our control, in this case whether THA surgery was cancelled or not due to the COVID-19 pandemic and the resulting scarcity of operating rooms for THA surgery.

An important step in RCT emulation is to verify the validity of the assumption that a comparison between two groups (in our study patients who did and who did not undergo THA surgery within the COVID period) is indeed (pseudo)random and requires analysis. The answer to this question is an outcome of the research, not something we can determine with certainty in advance.

Therefore, the aim of this study is to measure if THA is effective in restoring physical function in patients with osteoarthritis of the hip compared to non-surgery in existing Value-Based Health Care (VBHC) data by means of RCT Target Trial Emulation.

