3. METHODS

3.1 Study design

Hip osteoarthritis patients eligible for THA and placed on the waiting list for surgery will be included when the preoperative intake questionnaire is completed between 1-4-2020 and 1-1-2022. In a retrospective dataset we compare two standard care strategies: THA and wait-and-see, in which patients did not receive THA and remain on the waiting list. Patients were assigned to one of the two groups based on

whether surgery could be performed or whether THA was cancelled and patients remained on the waiting list. The first group (THA group) consists of patients that received surgery before 1-1-2022 and completed a 3-months postoperative questionnaire before 1-4-2022. The second group (control group) consists of patients which did not receive surgery before 1-1-2022 and completed a waiting list questionnaire before 1-4-2022. The target trial and emulation plan are shown in Figure 1 and the time-schedule of the emulation trial is shown in Figure 2. Patients that received THA on both sides between 1-4-2020 and 1-1-2022 will be excluded. The response rates on follow-up questionnaires will be reported for both groups. We will compare characteristics (age, sex, PROM-outcomes at baseline and physical therapy before the hospital visit) for patients that completed the follow-up questionnaires (completers) and patients that did not complete the follow-up questionnaires (non-completers). In the primary analysis we will correct for patient characteristics.

Target trial → Emulation

[figure not shown]
[figure not shown]

Figure 2: Timeline target trial emulation

THA= Total Hip Arthroplasty

FU = Follow-up

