In this study we compare the effect of THA compared to non-surgery on hip disability measured with the HOOS-PS change score from baseline up to approximately 3-months by means of RCT Target Trial Emulation, which aims to mimic a traditional RCT. Function and pain as a secondary outcome are measured by means of patient reported outcome measures (PROMs) pre-operatively and post-operatively or post-waiting list. The pre-operative intake questionnaire and the 3-months postoperative questionnaire are part of standard care. The waiting list questionnaire was administered during the Covid-19 pandemic to monitor patients' health status in two Santeon Hospitals (OLVG and Martini) in all patients who were at least three months on the waiting list. Therefore our study will be performed with data of these two Santeon Hospitals. All data is available through the routinely collected data for hip osteoarthritis within the VBHC program and in addition the outcomes of the administered waiting list questionnaire. Therefore, it is not needed to obtain additional information from patients.

To test the assumption that group allocation is (pseudo)random and cannot be explained by patient characteristics or severity of pain and hip disability at baseline, a logistic regression analysis will be performed on patients within the VBHC data set between 1-4-2020 and 1-1-2022. Group being the dependent variable (THA vs. non-surgery) and age (continuous), sex (M/F), physical therapy before the hospital visit (yes/no), follow-up time in days (continuous), pain at baseline (NRS, continuous) and the HOOS-PS at baseline (continuous) will be included in the model as independent variables. Secondly, we will test the assumption that follow-up time in days is not statistically significantly different between the THA and non-surgery group. Follow-up time is defined by calculating the number of days between the date of the orthopedic visit) and the date of the follow-up questionnaire. Results will be considered statistically significant when $p \leq 0.05$. In case an independent variable has a statistically significant effect on group assignment and/or follow-up time in days is significantly different between the two groups, clinical relevance will be considered and discussed within the research team, for example the effect size on chance to be allocated to the THA or non-surgery group.

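### Two hospitals are pooled but hospital is in no model, variable list or planned table, so the allocation check does not test whether the groups are balanced across hospitals

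*Combined protocol and SAP*

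**What the plan says.** Section 3.1 explains that the waiting-list questionnaire was used in two hospitals and concludes: "Therefore our study will be performed with data of these two Santeon Hospitals". Section 1.2.3 admits patients from either hospital, and 1.2.1 names "the VBHC data analysts at OLVG and Martini hospital" among those who collect the data.

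Hospital then drops out of the plan:

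- **Outcome models (1.4.2, item 1).** The independent variables are "experimental condition (THA/ no-THA), age, sex, HOOS-PS score at baseline, pain score at baseline, physical therapy before baseline (yes/no) and follow-up time in days".
- **Allocation check (3.1 and 1.4.2, item 2).** A logistic model of group is fitted "to check whether the group allocation cannot be explained by patient characteristics". Its terms are age, sex, prior physical therapy, follow-up time, baseline pain and baseline HOOS-PS.
- **Variable table (1.3.2).** There is no hospital or site row. The only row that contains the word hospital is the one on prior physical therapy.
- **Response and completers (3.1).** "The response rates on follow-up questionnaires will be reported for both groups". Then: "We will compare characteristics (age, sex, PROM-outcomes at baseline and physical therapy before the hospital visit") between completers and non-completers. Neither is broken down by hospital.
- **Descriptives (1.4.2).** These cover the models' independent variables, so hospital is not among them.

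The Introduction says: "An important step in RCT emulation is to verify the validity of the assumption" that the comparison of the two groups is (pseudo)random. The end of 3.1 makes the causal claim conditional on patient characteristics not affecting allocation and on similar follow-up time.

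**The concern.** In a two-site observational comparison, site is an obvious candidate for imbalance. It could arise here in two ways.

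1. Operating capacity may have been cut differently at the two hospitals. The Introduction gives an example of a patient whose operation "had to be rescheduled due to changed government or regional policy effective the next day".
2. Group membership under 3.1 requires a completed follow-up questionnaire, and the two groups complete different ones. If response differed between hospitals in one group only, the hospital shares would drift apart.

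If hospital also related to change in HOOS-PS or pain after the planned adjustment, the THA effect would be biased. A reader of the planned output could not judge this. The plan does not commit to counts by hospital or to a hospital-adjusted estimate, and a clean allocation check would not address the question.

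**Working it through.** The plan gives no figure to reproduce: it states no hospital shares, no between-hospital difference and no standard deviation.

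**Step 1: does the planned check respond to hospital imbalance?** The planned logistic model was simulated with 100 per group (1.2.2 expects at least 100), 600 runs, and hospital assumed unrelated to the six covariates.

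| Hospital share, THA / control | Joint test of planned check rejects | Hospital term, if added, has p ≤ 0.05 |
|---|---|---|
| 50% / 50% | 7% | 5% |
| 60% / 40% | 5% | 83% |
| 70% / 30% | 4% | 100% |
| 80% / 20% | 6% | 100% |

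The planned check rejects at about its nominal rate whatever the split.

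**Step 2: possible size of bias.** All inputs are assumptions except the thresholds of 23 and 2 points (1.4.2) and the 100 per group. Bias = d × h, where d is the difference in hospital share between groups and h is the residual hospital effect on the change score.

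- HOOS-PS, d = 0.1 to 0.4, h = 3 to 8: 0.1 × 3 = 0.3 to 0.4 × 8 = 3.2 points, in either direction. 0.3/23 = 1%; 3.2/23 = 14%.
- NRS pain, h = 0.3 to 0.8: 0.1 × 0.3 = 0.03 to 0.4 × 0.8 = 0.32 points. 0.03/2 = 1.5%; 0.32/2 = 16%.
- If h = 0, the bias is 0 at any d.

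For comparison, SE = SD × √(2/100). With SD 15 to 20 for HOOS-PS, SE is 2.12 to 2.83 and the 95% half-width 4.2 to 5.5. With SD 2 to 3 for NRS, the half-width is 0.55 to 0.83.

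The range depends on the inputs. With h = 5 to 15 and shares from 60/40 to 80/20 (d = 0.2 to 0.6), the same product gives 1 to 9 points.

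**Step 3: when could it change a conclusion?** With SD 18, SE = 2.55, and the chance that the HOOS-PS estimate exceeds 23 is 1 − Φ((23 − true − bias)/2.55), with effects expressed as improvement.

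| True difference | Bias −3.2 | No bias | Bias +3.2 |
|---|---|---|---|
| 15 | <0.1% | 0.1% | 3% |
| 22 | 5% | 35% | 81% |
| 30 | 93% | 99.7% | 100% |

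At a true 22 with a bias of 1 point, the chances are 22%, 35% and 50%.

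**Step 4: could response alone produce imbalance?** Assume equal starting shares and, among controls only, response of 80% at one hospital and 60% at the other. The control share becomes 0.80/(0.80 + 0.60) = 0.571 against 0.50, a 7-point difference. With 80% and 50% it is 0.615, a 12-point difference.

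**Step 5: what does adding hospital cost?** Take group and hospital each split 50/50 overall.

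| Share difference d | SE multiplier 1/√(1 − d²) | Multiplier of other residual bias if hospital drives only allocation, 1/(1 − d²) | SD of the chance difference between the two estimates, h = 0, SD 18 (HOOS-PS points) |
|---|---|---|---|
| 0.1 | 1.005 | 1.01 | 0.25 |
| 0.2 | 1.021 | 1.04 | 0.53 |
| 0.4 | 1.091 | 1.19 | 1.11 |

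**The case against.** A reader might infer that a clean allocation check says nothing at all about hospital balance. That holds only if hospital is unrelated to the six covariates, as Step 1 assumes. If case mix or follow-up time differed between hospitals, the check would carry weak indirect information. It still would not test hospital balance.

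A reader might also infer that the THA effect is confounded by hospital. The documents do not support that. The regional-policy wording sits in an example that contrasts two operation dates, not two hospitals. The surgeon-quarantine example fits chance within one hospital, and the Introduction calls the scale-downs nationwide. Nothing links hospital to change in HOOS-PS or pain. Both sites feed the same data programme and used the same waiting-list questionnaire, and baseline scores are already adjusted for.

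Omission can be defended too. The check is openly limited to patient characteristics and follow-up time, so the plan does not contradict itself. If hospital affected only allocation, that would be part of the natural experiment; adjustment would then remove no bias, widen the interval and slightly amplify other residual bias. The two estimates will also differ by chance, so comparing them may not settle the matter.

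Most of this stands, and it is why the point is minor. It does not justify leaving the hospital split unreported when the plan itself treats verifying (pseudo)randomness as important. Figure 1, the emulation plan, is not shown in the text available and might mention site; the point rests on the printed lists.

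**Conclusion.** The point holds as a minor one. Confidence is high that hospital is absent from every printed model, variable and reporting list, and that the allocation check as printed does not test balance across the two hospitals. Confidence is low that this causes bias: both an allocation link and an outcome link would be needed, and the documents neither show nor exclude either. Every bias size above is an assumption. On the 0.3 to 3.2 point range, bias stays below the HOOS-PS confidence half-width, could change the reading only when the true difference is near 23 points (or near 2 points for pain), and is unlikely to reverse a large effect. Larger assumed inputs would widen that zone in proportion.

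**What to change.** 1. Add hospital (two levels) to table 1.3.2.
2. Tabulate group by hospital as counts and shares, with a 95% CI for the difference in share. Give the already planned response rates by hospital within group.
3. Add hospital as a two-level fixed effect to the allocation model and to both outcome regressions, and report the THA effect with and without it.
4. Do not judge balance by a p-value alone. At 100 per group, a two-sided 5% test has 29% power for 55% against 45% and 81% for 60% against 40%; the CI half-width is about 1.96 × √(2 × 0.25/100) = 0.14.
5. State in advance that a small shift between the two estimates is not evidence of confounding (Step 5).

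The cost is a few lines of text, two small tables, one degree of freedom per model and an SE larger by about 0.5% to 9% for share differences of 0.1 to 0.4. If hospital affects only allocation, the term removes no bias and multiplies other residual bias by about 1.01 to 1.19, which is the reason to show both estimates. Hospital is known from eligibility and from the site analysts. It should be requested at extraction: 2.2 says the data will be used anonymously, so a field left out may be hard to restore later.

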1. INTRODUCTION

Total hip arthroplasty (THA) is one of the most frequently performed orthopedic surgeries. Studies show that THA is an effective treatment to reduce pain and to improve hip function and quality of life in patients with osteoarthritis of the hip. However, the effectiveness of THA has never been investigated by means of a randomized controlled trial (RCT), which is the gold standard to assess effectiveness of an intervention.

During the Covid-19 pandemic, elective orthopedic interventions were defined as not urgent and therefore cancelled. The National Institute for Public Health and the Environment (RIVM) estimated that in 2020 and 2021 in total 32,000 Quality-Adjusted Life Years (QALYs) were not realized due to postponing THA in patients with osteoarthritis of the hip in the Netherlands (9, 10). Better understanding of the treatment effect of THA, compared to non-surgery, could help improve prioritization of interventions.

The ideal research design to investigate effectiveness of THA would be to randomize patients between surgery and (delayed) non-surgery. Such an RCT is deemed unethical due to the effect size of THA shown in observational studies. It is considered unethical to withhold the patients who are allocated to the conservative treatment from the apparent benefits of THA. The required investments in time and money to perform an RCT and expected difficulty to include sufficient patients do not outweigh the benefits of measuring the effect of THA to demonstrate its urgency. Moreover, a potential benefit of research with observational data is, that it better reflects real-world data.

During Covid-19, there were different phases of hospital reduction and restoring of surgical capacity. During periods when surgeries were scaled down nationwide, only emergency surgeries for fractures, infections, and revisions were performed in the orthopedic department. However, our study specifically

focuses on elective primary total hip replacements for osteoarthritis, and during the research period, there was no prioritization based on the severity of symptoms within this osteoarthritis population.

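### Both outcome models impose one baseline slope on operated and waiting patients, so the single THA coefficient need not equal the average effect and cannot show how the effect varies with baseline severity

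*Combined protocol and SAP*

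**What the plan says.** Section 1.4.2, item 1, sets out the outcome models in full: "Two multiple regression analyses will be performed with the HOOS-PS and pain change score, respectively, as the dependent variable". The independent variables are "experimental condition (THA/ no-THA), age, sex, HOOS-PS score at baseline, pain score at baseline, physical therapy before baseline (yes/no") and follow-up time. No product term is listed. The resulting group differences are called "clinically relevant when differences exceed the MCID of 23 points for the HOOS-PS and 2 points for the NRS".

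The primary outcome is a "Rasch-based interval score ranging from no difficulty (0) to extreme difficulty (100") according to section 1.3.1. For the secondary outcome, section 3.5.2 says: "Pain during weight bearing is measured on a numerical rating scale (NRS) ranging from 0-10".

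Four other places bear on the point:

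- The Introduction leaves open whether allocation was as good as random and treats that as a finding of the study.
- Section 3.1 hypothesises that baseline severity does not influence allocation and plans a logistic regression to test it. It also adjusts for patient characteristics in the primary analysis.
- Section 1.2.2 expects a minimum of 100 patients per group and fixes no ratio.
- Section 1.3.1 adds an anchor-based minimal important change, which does not give the THA effect by baseline score.

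Nowhere is a THA-by-baseline term, a standardised effect or an effect at given baseline levels planned.

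**The concern.** An improvement on either scale cannot exceed the patient's baseline score. If surgery brings most patients close to the good end, their change will follow their baseline closely, while waiting patients stay nearer their own starting value. Follow-up scores would then rise less steeply with baseline after THA than on the waiting list, and the THA effect would grow with severity. A model with one slope averages over this, and the weights it uses depend on group sizes and baseline spread.

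Two things are at stake. The first is whether the reported coefficient is the average effect in the patients analysed. The second holds even in perfectly balanced groups: a single number set against 23 (or 2) points says nothing about how the mean effect differs between mild and severe patients.

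**Working it through.** The plan states no effect size, SD, slope or allocation ratio, so there is no figure of its own to reproduce.

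**Inputs from the documents.** The model terms and thresholds (1.4.2), the score ranges (1.3.1 and 3.5.2), and the minimum of 100 per group with no ratio (1.2.2).

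**Inputs assumed.** Slopes of follow-up score on baseline, baseline means and SDs, the baseline gap, the share operated p, and the residual SD. Baseline is already in the model, so using change instead of follow-up score lowers both slopes by 1 and leaves the THA coefficient and the slope difference unchanged.

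**Formula (one baseline covariate).** Let the slopes be b1 (THA) and b0 (waiting), the baseline means m1 and m0, and the baseline SDs s1 and s0.

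- The common slope is w·b1 + (1-w)·b0, with w = p·s1² / (p·s1² + (1-p)·s0²).
- The THA coefficient is then the effect at baseline (1-w)·m1 + w·m0.
- The average effect is the effect at p·m1 + (1-p)·m0.
- Coefficient minus average = (b1-b0)(1-w-p)(m1-m0).
- With equal variances w = p, which gives (b1-b0)(1-2p)(m1-m0).

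**Numbers.** Slopes 0.3 and 0.7 (difference -0.4), equal variances, operated group worse at baseline:

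| Share operated | 1-2p | Gap 5 points | Gap 8 points |
|---|---|---|---|
| 50% | 0 | 0 | 0 |
| 75% (300 vs 100) | -0.50 | 1.0 | 1.6 |
| 83% (500 vs 100) | -0.67 | 1.3 | 2.1 |
| 85% | -0.70 | 1.4 | 2.2 |

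Lower scores are better, so a positive departure understates the benefit. The sign reverses if the operated group is milder at baseline or is the smaller group. With no baseline gap the departure is 0 for any slopes and any p.

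**Simulation, scores clipped to 0-100.** With baseline SDs of 15-16 and the slopes above, the departure was about 1.0-1.7 points at 300 vs 100 and 1.3-2.1 at 500 vs 100. In a second set (slopes 0.2 and 0.7, SD 17 in both groups, p = 0.75, gap 5), the single coefficient was -29.09, the centred-interaction coefficient -30.32 and the true average -30.40. Over a wider grid (slope differences 0.3 to 0.8, gaps of 5 and 10, p from 0.25 to 0.75) the departure reached 4.5 points in size. That extreme needs slopes 0.1 and 0.9, a 10-point gap, 75% operated and SDs 17 and 14. The interaction model stayed within about 0.2 points of the average throughout.

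**Scale.** For an assumed residual SD of 13 to 20, the 95% CI half-width is 1.96 x SD x √(2/100) = 3.6 to 5.5 points at 100 vs 100. At 300 vs 100 it is 1.96 x SD x √(1/300 + 1/100) = 2.9 to 4.5.

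**Effect by baseline.** A slope difference of 0.3 to 0.8 makes the mean THA effect differ by 12 to 32 points between baselines 30 and 70 (difference x 40). With slopes 0.2 and 0.7 and an effect of -25 at baseline 50, it is -15 at 30 and -35 at 70. It passes 23 points at baseline 46, from -25 - 0.5(x - 50) = -23.

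**Can the term be estimated?** At 100 per group and baseline SD 17, power for a slope difference of 0.5 is about 96% to 99.6% (residual SD 16 or 13). For 0.3 it is about 62% to 79%.

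**The case against.** The best defence is the protocol's own hypothesis. If baseline severity is unrelated to allocation, the main-effects coefficient is still consistent for the average effect, however different the slopes. The same holds with equal group sizes and equal baseline variances. Any dependence of change on baseline that both groups share is already absorbed by the baseline term, and the score bounds make unequal slopes plausible without proving them. All of this stands. A reader might infer that the planned coefficient is simply wrong; the documents do not support that.

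The size is also open to challenge. With the minimum of 100 waiting, 75% or 85% operated means 300 or about 567 operated patients, and nothing in the plan points to either. If mean scores were about 18 after THA and 52 on the waiting list (assumed), the effect would be about 34 points, and an error of 1 to 2 would leave it far from 23. The coefficient also always lies between the effect in operated patients and the effect in waiting patients, and the plan names no target population that would make that weighting an error. These points limit the severity.

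The planned allocation check gives only partial protection. With 300 vs 100 and SD 15, a 5-point gap gives z = 5 / (15 x √(1/300 + 1/100)) = 2.9, so it would usually be noticed. At SD 15 to 17 a simple comparison would still miss it about 18% to 28% of the time. When it is noticed, the planned response is discussion, not a changed model.

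Two further inferences are tempting and should not be drawn. The 23 points are applied to a between-group difference. An interaction gives mean effects by baseline, not which individual patients improve by 23. And the Introduction's remark that better knowledge "could help improve prioritization of interventions" concerns the standing of THA among interventions, as section 4.1 confirms; no section proposes ranking patients by severity.

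**Conclusion.** The point holds as a conditional robustness and reporting gap. The common-slope coefficient departs from the average THA effect only if three things coincide: different slopes, a baseline gap, and unequal group sizes or baseline spread. The plan can exclude none of them in advance. The departure is zero under the protocol's allocation hypothesis and about 1 to 2 HOOS-PS points under moderate assumed values with 75% to 85% operated. It exceeds 4 points only at the extreme of the assumptions. In the pain model the same formula gives 0.4 x 0.5 = 0.2 NRS points per point of baseline gap at 75% operated, again with an assumed slope difference of 0.4.

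This is no evidence that the primary conclusion would reverse. The lack of any estimate of how the mean effect varies with baseline does not depend on imbalance and may be the larger loss. Every size given here rests on assumed slopes, SDs, gaps and shares.

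**What to change.** Before the outcome analysis, add to section 1.4.2, item 1:

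- A THA x baseline-score term in each model: HOOS-PS centred at the pooled mean in the function model, and NRS pain centred at the pooled mean in the pain model.
- The THA effect standardised to the baseline distribution of all analysed patients, with robust standard errors, reported alongside the main-effects coefficient. In this linear model it is the THA coefficient after centring. State in advance which of the two is set against 23 and 2 points.
- The mean THA effect with 95% CI at the 25th, 50th and 75th percentiles of baseline, described as mean differences at those levels.

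No new data are needed. The cost is one extra parameter per model and slightly wider intervals away from the mean baseline. In simulation with equal slopes the standard error of the average effect rose by at most about 5%. The change does not address unmeasured confounding or differences in follow-up time.
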